3.1.4 Model assessment of stage 2 analysis

The primary analysis model will be assessed for model fit and outlying or influential observations as per methods described below.

To determine the fit of the model by using summary measures of goodness of fit and by assessing the estimation ability of the model:

- i. Perform the goodness-of-fit test using the Hosmer-Lemeshow test to look at the discrepancy between the observed and estimated frequency of outcomes (Stata command *estat gof*).
- ii. Examination of the ROC curve (Stata command *lroc*) to assess the correct identification of outcome based on varying probability thresholds.
- iii. Plot of the Pearson's standardised residuals (*predict.., rstand*) against predicted values (*predict..*). Plots showing trends suggest poor model fit or misspecification of model.

If model assumptions are deemed to be invalid or the model appears to be miss-specified, we will undertake a sensitivity analysis with an alternative model.

To determine if there are any observations that do not fit the model or have a large influence on the model:

- i. Check for outliers/predicted values that have poor fit by plotting deviance residuals (*predict* ..., *deviance*) against predicted values (*predict* ...); standardised Pearson's residuals (*predict* ..., *rstand*) against predicted; and leverage (predict ..., hat) against predicted.
- ii. Investigate whether the extreme outlying observations have been recorded correctly and if so, compare model coefficient estimates with and without the identified influential observations
- iii. Use Cook's distance (stata command predict.., cook) to identify influential observations

3.1.5 Stage 2 exploratory analysis for primary outcome

i. Co-enrolment at time of randomisation

An exploratory analysis of the primary outcome will be undertaken in order to assess the impact of co-enrolment to an 'active'* arm of another study at the time of or prior to randomisation into MATIS (includes day of randomisation or one day post randomisation). Individual treatments will be included as separate covariates in the primary analysis model described above. In the event of low event rates the sensitivity analysis will be repeated removing one covariate at a time.

*We will only consider those co-enrolled to an 'active' arm of another study. Co-enrolment to the standard of care arm in other studies will not be considered an active treatment.

ii. Co-enrolment post randomisation and receipt of rescue medication

We will explore what the direct effect of the treatment is on the outcome, and whether there is an indirect effect of receipt of active treatment as a result of co-enrolment when occurring post-randomisation, and receipt of known effective treatments dexamethasone, tociluzimab, paxlovid and molnupiravir post-randomisation (>1 day post randomisation). Where post-randomisation co-enrolment or receipt of known effective treatments must occur prior to the occurrence of the outcome. We will do this via a mediation analysis using a structural equation modelling approach using the Stata *paramed* command.^{7, 8}

The analysis will allow us to decompose the total observed treatment effect into mediated (indirect, described by the natural indirect effect in the Stata output) and non-mediated (direct, described by the natural direct (and controlled direct effect) effect estimate in Stata output) components. Each post-randomisation active intervention and known effective treatments will be treated as an individual mediator, thus we will estimate the mediated effect separately for each. Analysis models will adjust for baseline WHO COVID-19 score (3 or 4), age (<65 or ≥65), receipt of known effective treatments dexamethasone and/or tociluzimab, prior vaccination against COVID-19, and receipt of paxlovid and/or molnupiravir at the time of or prior to randomisation into MATIS and site as fixed as per the primary analysis model described in section 3.1.3. The model will be modified in a similar manner as the primary outcome modelling in the event of low event rates.

iii. Compliance

We will undertake an exploratory analysis to examine the treatment effect (reported as a risk ratio (RR)) adjusted for compliance. This will be achieved through a complier adjusted case (CACE) analysis using a two-stage residual inclusion estimator (2SRI) approach with randomisation group as the instrumental variable. The primary analysis model described in 3.1.3 will be refitted with the log link function (instead of logit function) to give the treatment effect as a RR with corresponding 95% confidence interval and p-values. The CACE will then be estimated for this model and we will compare the CACE estimates of the RR to the RR obtained from the refitted primary analysis model. Randomisation meets the criteria for an adequate instrument variable since (i) randomisation predicts the treatment receipt, (ii) randomisation is unconfounded with the outcome and we assume (iii) no direct effect of randomisation on the outcome (other than via treatment receipt) – *the exclusion restriction*. After the second stage of estimation, the standard errors of the estimates will be corrected using the method of Terza. ^{9, 10}

This approach can only include adherence information in the intervention groups as the equivalent usage in the control participants is not recorded (as the control intervention is SOC and can differ between participants and is likely to evolve with time). SOC will be assumed to be 100% compliant with prescribed treatment.

We will define a complier as an individual who receives $\geq 90\%$ of prescribed dose. In addition to the analysis using a 90% threshold to define compliance we will undertake alternative analysis defining a 'complier' as an individual who receives $\geq 60\%$, $\geq 70\%$ and $\geq 80\%$ of prescribed dose to explore the impact of alternative definitions of compliance.

Analysis will adjust for baseline WHO COVID-19 score (3 or 4), age (<65 or ≥65)), receipt of known effective treatments dexamethasone and/or tociluzimab, prior vaccination against COVID-19, and receipt of paxlovid and/or molnupiravir at the time of or prior to randomisation into MATIS and site as fixed as per the primary analysis model described in section 3.1.3. The model will be modified in a similar manner as the primary outcome modelling in the event of low event rates.

iv. Time of enrolment

An exploratory analysis of the primary outcome will be undertaken in order to assess the impact of time of enrolment. A categorical variable will be created by splitting the recruitment period into quartiles such that participants are grouped into approximately four equal sized groups based on time of enrolment into the MATIS study. This variable will then be included as a covariate in the primary analysis model described above as a treatment group-by-time interaction term to assess the impact of time of recruitment on the treatment effect estimate.

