In Stage 2 a logistic regression model will be used to assess the treatment effect of RUX and FOS compared to SOC. The model will include the treatment arms, baseline modified WHO Severity Score, trial co-enrolment at baseline, and randomisation stratification variables viz. site and age (<65 vs ≥65). As well as reporting OR and 95% CIs, the model will be used to estimate the difference in proportion of participants with modified WHO COVID-19 Ordinal Score ≥5. The treatment effect in the absence of post-randomisation co-enrolment and receipt of rescue medication will be estimated in a supplementary analysis where participants' outcomes after either will be treated as missing and a controlled multiple imputation using a delta based approach will be used.

For the primary outcome, progression to severe COVID-19 disease within 14 days, discharge alive from the admitting hospital before 14 days will assume safety from the event (in the absence of additional data confirming otherwise). An additional sensitivity analysis will be performed if there is a change of dose after review of the first thirty patients.

For time-to-event analyses required for secondary endpoints such as time to discharge, each treatment group will be compared with SOC and modelled using a proportional hazards time-to-event model adjusted for randomisation stratification variables. Kaplan-Meier estimates for the time to event will also be plotted (with confidence intervals). The log-rank 'observed minus expected' statistic (and its variance) will be used to estimate the average event rate ratio (and its confidence interval) for those allocated to each treatment group versus the no additional treatment group.

Pre-specified subgroup analysis will be conducted for the primary outcome using the statistical test for interaction (or test for trend where appropriate) for the following: disease severity as graded by the WHO

MATIS version 4.0 dated 2nd November 2022

IRAS: 282552 Page **28** of **57** 

Imperial College Healthcare

COVID-19 Ordinal Severity Scale; time since onset of symptoms; sex; age; and comorbidities obesity, chronic heart, lung, kidney and liver disease, diabetes, immunocompromised and smoking status. Pre-specified subgroup analyses will also be conducted for the primary outcome using the statistical test for interaction (or test for trend where appropriate) for patients with admission CRP >200mg/L and/or D-dimer 2500ng/mL.

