1.5.1 Sample size for formal interim analysis (Stage 1)

Current rate of severe pneumonia in the standard of care is 50%. In the case that an experimental arm reduces this to 30% (relative risk, RR, 0.6), then the design provides a 92% chance (one-sided alpha of 0.25, equivalent to stopping for futility if the one-sided p-value is >0.25) of it being recommended to continue to stage 2.

The design recommends stopping an intervention arm at stage 1 if the one-sided p-value is >0.25 but this is a non-binding rule (i.e. the overall power is calculated assuming this rule is always followed and the family-wise error rate (FWER) is calculated assuming it is not followed). The actual FWER will be lower if the rule is always followed).

Recruitment to the trial will continue during this interim analysis stage.

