1.5.2 Sample size for full trial (Stage 2)

If the trial is recommended to continue at Stage 2 based on DMC interim review, the full trial will need to recruit an additional 95 for each arm that continues (152 per arm in total; 456 to the complete trial). This will provide 90% power to detect a change of RR of 0.6 (50% to 30%), with one-sided alpha of 0.027 (chosen to give a 5% FWER) and has been inflated by 5% for missing outcome data. Here the power is the chance of an effective treatment passing stage 1 and being recommended after stage 2.

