Every effort will be made to obtain follow-up data for all participants including those that stop treatment. The number and proportion of participants missing WHO COVID-19 status by treatment group and visit will be tabulated (see section 2.5 above). For participants who are discharged early the assumption will be made that they did not progress to grade 5 WHO scale. If there is a >5% rate of missing outcomes after this, we will impute missing WHO COVID-19 data in the primary analysis model using multiple imputation under the assumption of missing at random (MAR). That is the probability of being missing is not dependent on the values of unobserved data, conditional on the observed values of the variables included in the analysis model. Imputation under MAR using chained equations following the guidance of White et al. will be undertaken.⁴ Variables in the imputation model will include the variables in the primary analysis model described above plus baseline WHO COVID-19 score (3 or 4), age (<65 or ≥65), receipt of dexamethasone and/or tociluzimab at the time of or prior to randomisation into MATIS. Additional auxiliary variables that are suspected to be associated with the outcome and are predictors of missingness will also be included. These are receipt of any effective treatments post randomisation as a result of co-enrolment when occurring postrandomisation, and receipt of known effective treatments dexamethasone and tociluzimab postrandomisation (>1 day post randomisation) and WHO COVID-19 scores at day 1 and day 7. Using White et al.'s rule of thumb we will impute m datasets based on the percentage of participants with incomplete outcomes, where m will be rounded to the nearest 10, for example if 8% of participants have incomplete primary outcome then m=10 will be used.

Before undertaking the multiple imputation as described above we will impute any missing baseline data deterministically only using other baseline data, this includes the baseline WHO COVID-19 status, age, receipt of dexamethasone and/or tociluzimab at the time of or prior to randomisation into MATIS. To do this we will impute missing values with the mean values of observed data. In line with White et al., outcomes will be imputed separately for each treatment group.

Imputed datasets will then be analysed using the primary analysis model described above.

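### SAP 3.1.5 ii omits the protocol's no-rescue estimate and plans one-agent-at-a-time mediation models that can credit part of a real drug effect to rescue

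*SAP*

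**What the plan says.** Protocol 4.2 gives both a target and a method. The target: "The treatment effect in the absence of post-randomisation co-enrolment and receipt of rescue medication will be estimated in a supplementary analysis". The method: outcomes seen after either event count as missing and are filled by delta-based controlled multiple imputation. Section 4.2 leaves further detail to the SAP, and Protocol section 7 says that rescue and co-enrolment will be allowed for in the analysis.

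SAP 3.1.5 ii uses Stata's paramed command to split the total effect into natural direct and indirect components, and also lists a controlled direct effect. The mediators are active treatment through later co-enrolment, and dexamethasone, tocilizumab, Paxlovid or molnupiravir received more than one day after randomisation. Each of these "will be treated as an individual mediator, thus we will estimate the mediated effect separately for each". A timing rule applies: "Where post-randomisation co-enrolment or receipt of known effective treatments must occur prior to the occurrence of the outcome". Adjustment covers baseline WHO score, age group, vaccination, the listed treatments up to day 1, and site.

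The "WHO COVID-19 scores at day 1 and day 7" enter the imputation model for missing primary outcomes (SAP 3.1.2, carried into stage 2 by 3.1.3) but not the mediation models. Nowhere does the SAP set outcomes to missing after rescue or apply a delta adjustment, and it states no assumption about common causes of rescue and outcome.

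**The concern.** Protocol 2.1 expects these drugs to work by averting deterioration, and both documents call the later treatments rescue. If deterioration short of the endpoint prompts rescue, it is a common cause of rescue and outcome, and the drug itself changes it. Natural direct and indirect effects are not identified under that structure, and baseline adjustment does not help. Within an arm, rescued patients then do worse because they had already worsened. Fewer rescues on the drug therefore look like a pathway of drug action even if rescue has no effect.

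Two features add to this. Agents given to the same worsening patients each pick up the same artefact when modelled singly. The timing rule also records a patient who progresses quickly as unrescued.

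The trial is open label and supportive care is at the physician's discretion (Protocol 3 and 7.10). Readers will ask whether rescue explains or masks the result, and 3.1.5 ii is the one inferential analysis of post-randomisation rescue that the SAP describes.

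**Working it through.** **1. Design figures.** SAP 1.5.1 and 1.5.2 give 50% vs 30%, 57 and 152 per arm, and 5% missing. Evaluable per arm: 57 × 0.95 ≈ 54 and 152 × 0.95 ≈ 144.
- Stage 1 at one-sided 0.25: pooled SE = √(2 × 0.4 × 0.6/54) = 0.0943; unpooled SE = √((0.25 + 0.21)/54) = 0.0923. The pass chance is Φ[(0.20 − 0.6745 × 0.0943)/0.0923] = 93.0%, or 92.3% on the log-odds scale. The SAP says "the design provides a 92% chance".
- Two-stage power, with correlation √(54/144) = 0.61 between stages: 89.4% (pooled), 89.9% (unpooled) or 88.3% (log odds), against 90%.
- Family-wise error at 0.027, futility rule ignored: 4.9%, against a 5% maximum.

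The design reproduces, so 50% vs 30% is a fair anchor. The mediation section has no figure of its own, and neither document gives rescue or worsening rates. All rates below are assumptions.

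**2. Closed-form example, rescue inert.** Worsening in 57% (SOC) and 29% (drug); rescue in 60% of worsened and 5% of other patients; endpoint in 80% and 10%. Because rescue is inert, the true indirect OR is 1 and the true direct OR equals the total.
- Rescue: 0.57 × 0.60 + 0.43 × 0.05 = 0.363 (SOC); 0.29 × 0.60 + 0.71 × 0.05 = 0.209 (drug).
- Endpoint: 0.57 × 0.80 + 0.43 × 0.10 = 0.499; 0.29 × 0.80 + 0.71 × 0.10 = 0.303. Total OR 0.436.
- Endpoint on drug: 0.681 if rescued, 0.203 if not. With the SOC rescue distribution: 0.363 × 0.681 + 0.637 × 0.203 = 0.377.
- Direct OR = odds(0.377)/odds(0.499) = 0.607. Indirect OR = odds(0.303)/odds(0.377) = 0.719.
- Share credited to rescue = ln 0.719/ln 0.436 = 40%.
- With rescue in 40% or 80% of worsened patients, direct OR is 0.521 or 0.724 and the share 21% or 61%.
- Controlled direct OR (no rescue, drug-by-rescue interaction allowed) = odds(0.203)/odds(0.351) = 0.471, against a truth of 0.436.

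**3. Simulation with another worsening model.** Two million patients; worsening in 45% (SOC) and 14% (drug); totals 50% vs 30%, OR 0.43; rescue inert. This uses the command's logistic-model formulas, so its figures are not interchangeable with step 2.

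| Rescue, worsened/not worsened | Indirect OR (truth 1) | Share of log OR | Controlled direct OR (truth 0.43) |
|---|---|---|---|
| 30%/20% | 0.99 | 1% | 0.44 |
| 40%/10% | 0.91 | 11% | 0.48 |
| 60%/10% | 0.80 | 27% | 0.55 |
| 80%/10% | 0.70 | 43% | 0.68 |

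- If half the drug effect acts through worsening, the shares are 1%, 6%, 13% and 20%.
- If rescue is unrelated to worsening, the drug does not change worsening, or the drug is null, the indirect OR is 1.00.
- At 144 per arm, the median indirect OR is 0.92 (40%/10%) or 0.81 (60%/10%), and it falls below 1 in 91% or 99% of simulated trials.

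**4. One agent at a time.** Two inert agents at 60%/10% each give an indirect OR of 0.80. Their shares sum to 53%, against 27% when modelled as any rescue.

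**5. Timing rule.** Steps 2 to 4 leave it out. In a day-by-day simulation (600,000 patients) that applies it, the share is about 0 to 54% if the drug acts through worsening, and about +5% to −23% if it acts otherwise. With the rule, rescue unrelated to worsening can still show a share of 4 to 5%.

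**6. The protocol's analysis.** In the step 3 settings, outcomes after rescue were set to missing and recovered from unrescued patients. With worsening in the model, the OR is 0.43 in all four rows. Without it, the OR is 0.45, 0.48, 0.55 and 0.68. In the step 2 example, if recorded severity detects only half of worsening, the OR is 0.479.

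**The case against.** Five points on the other side deserve weight.

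- The SAP also reports a controlled direct effect, nominally the drug effect without that agent. A reader might infer that no output approaches the protocol's question; that goes too far. In step 2 this estimate misses by about 9% of the log OR (1 − ln 0.471/ln 0.436). It is further out in most of step 3, and never covers all agents together.
- A reader might also infer that the plan will understate the direct effect, or that 40% is the expected error. The documents support neither. No passage says that each listed agent, or later co-enrolment, follows worsening. The 40% comes from a strong case with inert rescue, whereas the SAP calls these treatments known to be effective, and it leaves out the timing rule, under which the sign can reverse.
- This is not the only planned look at the problem. SAP 2.3 and 2.4 plan co-enrolment and standard-of-care summaries, with details in SAP I, which is not supplied.
- Protocol 4.2 also says, more loosely, that a supplementary analysis will adjust for later co-enrolment and rescue, and mediation might be argued to meet that. The following paragraph, however, names a specific target and method, which mediation does not meet.
- The SAP follows protocol 2.2, which is not supplied, so a deliberate departure cannot be shown. The current protocol carries the commitment, and the log entries for versions 3.0 and 4.0 mention no change to it.

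The protocol's method also has a weakness. Below the endpoint, the in-hospital WHO score separates only grades 3 and 4, so it may miss much worsening. That bears on how to write the fix.

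**Conclusion.** The concern stands in conditional form. The SAP lacks the joint no-rescue, no-co-enrolment estimate in Protocol 4.2. The mediation models in its place can misattribute a real drug effect if rescue follows worsening that the drug reduces. That condition fits the trial's rationale and the word rescue, but no data in the documents establish it.

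The size is an assumption: about 0 to 60% of the log odds ratio across the illustrations. Without the timing rule it is zero if rescue is unrelated to worsening or the drug does not change worsening. With the rule it can reverse when the drug acts by another route. The controlled direct effect softens the problem without removing it. The section is exploratory, so the primary intention-to-treat test, alpha and sample size are untouched. What is at risk is the interpretation of the primary result.

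**What to change.** In SAP 3.1.5 ii, reinstate the protocol's analysis:
- Set the outcome to missing from the first rescue or post-randomisation active co-enrolment, for any listed agent jointly. Keep endpoints reached before that time.
- Impute from arm, baseline covariates and severity recorded before rescue: day 1 and day 7 WHO score plus FiO2, SpO2 and NEWS, all already in the visit schedule. Do not use a value recorded after rescue.
- Vary delta by arm, because unmeasured worsening may remain.
- Report rescue by arm with its timing, if SAP I does not already provide for this.

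Do not add post-baseline severity to paramed as an ordinary covariate. The drug affects it, and in simulation the controlled direct OR went to about 1.0 when the drug acted wholly through worsening. Keep the mediation results, if at all, as descriptive, and state that they assume no unmeasured and no treatment-affected confounding of rescue and outcome.

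The cost is SAP wording and one imputation run, with no new data. The interval will be wider and will rest on the delta assumptions: in the step 2 example, up to about 36% of SOC and 21% of drug outcomes would be imputed.

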#### 1.3 RATIONALE FOR THE STUDY POPULATION

Patients with COVID-19 infection in the community may be asymptomatic or experience only mild transient symptoms which do not merit experimental therapeutic intervention. Patients who are admitted to hospital due to the severity of their symptoms are invariably in the inflammatory phase of the disease with dyspnoea and/or hypoxia indicating involvement of the lower respiratory tract. Data from our own hospital as well as Chinese and Italian experiences indicate that around 30% of hospitalised patients will deteriorate during their admission resulting in the need for ventilatory support. The study population is therefore selected to evaluate whether the experimental treatments are effective in prevention of clinical deterioration in a hospitalised population.

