1.2 Trial design

A two stage, open label, randomized (1:1:1) controlled trial with formal interim analysis after 171 participants (57 per arm) which also includes an informal interim analysis after 30 participants (10 per arm) complete follow-up. Due to the three different stages in this trial, the MATIS SAP is separated into two sections. The aim of this statistical analysis plan (SAP) is to describe in detail the analysis that will be undertaken for the formal interim analysis and final analysis. The informal interim analysis was to provide an early opportunity to check the dosing regimen, see MATIS SAP I – Dose Verification for a detailed description of the statistical analysis conducted at this stage.

[figure not shown]

Figure 1: Schematic of study Design

Treatment is for 14 days from baseline. Patients will receive follow-up assessments at 1, 7, 14 and 28 days after the first dose. The time allowed for screening assessments allows time for eligibility assessments to be included.

- Screening Period: up to 7 days to the day of randomisation
- Treatment Period: 14 days
- Follow-up period: Day 14 to 28

Patients who have recovered and are fit for discharge from hospital during the treatment period, will be discharged home with trial medication to complete a fixed 14 day course. Such patients will be followed up weekly with telephone monitoring until day 28 and additional blood test monitoring where practically possible.

Table 1. Study visits

Table 1. Study visits	Screening	Baseline				Last
Study Day	-6 to 0	0	1+	7 #	14#	visit 28 #
Time window		-2 days	+1	± 3	± 3	± 3
		,	day	day	day	day
Informed consent	X					-
Inclusion/Exclusion criteria	X	X				
Demographic data	X					
Medical history including major	X					
comorbidities						
Physical exam	X					
COVID-19 diagnosis, duration and	X					
severity						
Pregnancy test	X					
Vital signs	X	X	X	X	X	X
NEWS score	X	X	X	X	X	X
Inflammatory markers (CRP, D-dimer,		X	X	X	X	X
LDH, ferritin, full blood count)						
PK levels*					X	X
Full blood count¶		Daily while on CYP3A4 inhibitor				
FiO ₂	X	X	X	X	X	X
SpO ₂ and/or PaO ₂	X	X	X	X	X	X
Randomisation		X				
Weight and Estimated height		X				
Safety monitoring of liver and renal	X	X	X	X	X	X
function						
Length of stay						
Serious Adverse Events	X	X	X	X	X	X
Concomitant medications	X	X	X	X	X	X
Serum		X		X		X
Plasma		X		X		X
RNA in PAX gene tube		X		X		X
PBMC		X		X		X
Nasosorption biomarkers		X		X		X

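### The compliance analysis uses a log-binomial refit that may not give usable risk ratios, and its only fallback is tied to low event rates, where the problem is smallest

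*SAP*

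**What the plan says.** SAP 3.1.3 fits a binomial model with logit link. It contains two treatment terms, baseline WHO grade, age group, dexamethasone, tocilizumab, prior vaccination, paxlovid, molnupiravir, and site as a fixed effect.

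SAP 3.1.5 iii labels the compliance analysis exploratory. The 3.1.3 model "will be refitted with the log link function (instead of logit function) to give the treatment effect as a RR". The complier effect is then estimated by two-stage residual inclusion (2SRI), with standard errors corrected by the Terza method, and "we will compare the CACE estimates of the RR to the RR obtained from the refitted primary analysis model". A complier is defined at 90% of prescribed dose, with alternatives at 60%, 70% and 80%.

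The section closes by allowing the model to be simplified as for the primary outcome when event rates are low. The simplifications in 3.1.3 are to drop site if its inclusion makes estimates unstable, to consider dropping the antivirals if few participants receive them, and then to use a propensity score. SAP 3.2.5 states what happens if a laboratory model fails to converge. SAP 3.1.5 iii has no such rule.

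On event rates, SAP 1.5.1 states: "Current rate of severe pneumonia in the standard of care is 50" per cent. It plans for 30% on an effective arm. Protocol 1.3 gives a different background figure: "around 30% of hospitalised patients will deteriorate during their admission resulting in the need for ventilatory support".

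**The concern.** Because the binomial family is kept and only the link is replaced, the refit is log-binomial. A log link multiplies risks and does not itself keep them below 1. When the average risk is high and the model has many terms, some covariate patterns are pushed to the limit. The likelihood maximum can then lie on the boundary, where the usual standard errors are not valid, or the fitting routine can fail to converge.

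Both risk ratios that the section sets out to compare depend on this model. The Terza correction is built on the same second-stage fit and inherits the problem. With no rule for this case, the analyst would have to choose a replacement after seeing the data.

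**Working it through.** **Plan figures.** The documents state no convergence rate, so there is none to reproduce. As a check on the event rates, the stage 1 power was recomputed with 57 × 0.95 ≈ 54 evaluable per arm: z = 0.20 / √[(0.5×0.5 + 0.3×0.7)/54] = 0.20/0.0923 = 2.167. Subtracting 0.674 (one-sided 0.25) gives 1.493, a power of 93.2% against the stated 92%. Overall two-stage power, with information fraction 57/152 = 0.375 and unpooled variance, is 90.0% against the stated 90%. The 50% and 30% rates are therefore the ones behind the design.

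**Where the boundary lies.** Under a log link, a pattern's risk is the arm's average risk times its risk ratio relative to that average. The risk reaches 1 when that ratio is:
- 1/0.50 = 2.0 on standard of care
- 1/0.30 = 3.3 on an effective arm
- 1/0.20 = 5.0 if the standard-of-care risk were 20%

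At 50%, three factors of 2^(1/3) = 1.26 each are enough. The margin shrinks as risk rises, so a low event rate is the easier case for this link.

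**Simulation.** From the documents: N = 456 ("152 per arm in total; 456 to the complete trial"), 1:1:1 allocation, 50% against 30% on both active arms, and the 3.1.3 covariates. Assumed, because the documents do not give them:
- prevalence of baseline grade 4 75%, age 65 or over 40%, dexamethasone 80%, tocilizumab 15%, vaccinated 30%, paxlovid 5%, molnupiravir 5%
- six unequal sites and 80% compliers
- covariate log-odds obtained by scaling a base odds ratio by factors from −1.0 to 1.5

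Each scenario has 120 data sets, so Monte Carlo error is at most √(0.5×0.5/120) = 4.6 percentage points. A careful fit means scoring with step-halving inside the region where all risks are below 1. Rows 1 to 7 give the percentage of data sets with a proper solution.

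| Fit | Base OR 1.0 | 1.5 | 2.0 | 3.0 |
|---|---|---|---|---|
| 1. Full refit, careful, 50% v 30% | 92.5 | 76.7 | 40.8 | 18.3 |
| 2. Full 2SRI second stage, careful | 89.2 | 78.3 | 44.2 | 19.2 |
| 3. Refit without site and antivirals | 99.2 | 97.5 | 90.0 | 72.5 |
| 4. Second stage without site and antivirals | 99.2 | 96.7 | 89.2 | 74.2 |
| 5. Refit with propensity score | 100 | 100 | 97.5 | 90.0 |
| 6. Full refit, careful, 20% v 12% | 97.5 | 99.2 | 92.5 | 84.2 |
| 7. Full refit, plain iterative least squares, 50% v 30% | 70.0 | 35.8 | 7.5 | 0 |
| 8. Log-link Poisson: any fitted value above 1, 50% v 30% | 11.7 | 41.7 | 91.7 | 100 |

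Rows 1 and 6 show that failure is more common at the planned rates than at low ones. A separate simulation at 432 evaluable participants, with its own assumed covariates and plain fitting, agreed in direction. The full model was valid in 68% of data sets with null covariates and 16% with strong ones, or 51% to 98% after dropping site and the antivirals. Log-link Poisson always converged there.

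**Repetition.** The refit and four compliance thresholds make five fits. If the analysis inherits the multiple imputation of 3.1.3, each must succeed in every imputed data set. With the SAP's example of m = 10, that is 5 × 10 = 50 fits.

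**The case against.** The documents give no covariate effects, so no failure rate can be claimed as expected. A reader might infer that the refit will usually fail. The documents do not support that: with null covariates a careful fit succeeds in 92.5% of data sets, and the SAP's own reductions raise success to between 72.5% and 99.2%. This stands. However, SAP 3.1.5 iii calls on those reductions only when event rates are low. Even where they are applied, up to 27.5% of refits still have no proper solution (100 − 72.5).

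A reader might also infer that the model returns probabilities above 1. A correctly maximised log-binomial fit cannot. It stops at a fitted risk of 1, and values above 1 come from fitting without step control. Poisson regression can also give fitted values above 1 (row 8), so that is not the ground for preferring it. Its advantages are reliable convergence and robust errors.

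Nor is 50% the overall event rate. It is the standard-of-care planning rate; the pooled rate under the design alternative is (50 + 30 + 30)/3 = 36.7%, and Protocol 1.3 cites about 30% for a narrower outcome. Lower risks ease the problem. The simulations at 50% v 30% already use the pooled 36.7%.

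**Conclusion.** The point holds as a minor gap in an exploratory analysis. The specified refit may not converge or may reach the boundary, so the intention-to-treat and complier risk ratios may not be obtainable with valid standard errors. The size depends on assumptions outside the documents: a careful full-model fit lacks a proper solution in about 7.5% to 81.7% of data sets at 50% v 30%, and in 0.8% to 27.5% after dropping site and the antivirals. These ranges rest on the assumed prevalences, covariate strengths, six sites and fitting routine.

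One part rests on the text and the arithmetic of the link alone: the fallback is tied to low event rates, although the log link is under more strain when risks are high. It would be wrong to infer any threat to the trial's main conclusion. The primary odds ratio, its p-value and the difference in proportions come from the logit model.

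**What to change.** Amend SAP 3.1.5 iii as follows:

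- Fit both the intention-to-treat risk ratio and the 2SRI second stage with a log-link Poisson model.
- Use robust (sandwich) standard errors for the intention-to-treat ratio.
- For the second stage, keep the Terza two-stage correction, built on the robust variance, or bootstrap both stages together. An ordinary sandwich at the second stage would ignore the uncertainty in the first-stage residuals.
- Extend the fallback trigger from low event rates to non-convergence or a boundary fit.
- If the intention-to-treat ratio is instead standardised from the 3.1.3 logistic model, standardise the complier ratio too, so that the two remain comparable.

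The cost is a few sentences in the SAP, with no change to data collection. Standard errors will be slightly wider than those of a valid log-binomial fit, and some Poisson fitted values may still exceed 1.
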